3.2 Secondary outcome variables

3.2.1 Complete renal response

To evaluate the effect of anifrolumab compared with placebo on renal response in LN subjects, the proportion of subjects achieving CRR at Week 52 will be used. A subject achieves CRR if **all** of the following criteria are met:

- Estimated glomerular filtration rate (eGFR):
 - ≥ 60 mL/min/1.73 m² or no confirmed decrease of eGFR from baseline of $\geq 20\%$
- 24-hour UPCR ≤ 0.7 mg/mg
- No discontinuation of IP or use of restricted medication beyond the protocol-allowed threshold before assessment. Allowed restricted medications are defined in [Appendix A](#) and [Appendix B](#).

The time to achieve CRR will be analysed as supportive analysis and will be derived as the date of first CRR minus the date of first dose of IP. If the subject did not achieve CRR, the time to achieve CRR will be censored at the earliest of the following:

- Date of withdrawal from the study;
- Discontinuation of IP in case of premature discontinuation of IP where the last IP dose is not in the Week 48 analysis visit window;
- Date of the latest of the Week 52 24-hour UPCR and eGFR observations used in analysis (or the date of the latest 24-hour UPCR or eGFR observation before Week 52 if the Week 52 observations are missing) in case of premature discontinuation of IP where the last IP dose is in the Week 48 analysis visit window;
- Date of the Week 104 24-hour UPCR and eGFR observations used in analysis (or the date of the latest 24-hour UPCR or eGFR observation before Week 104 if the Week 104 observations are missing);
- Database extract date.

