4.1.3 Presentation of results

All analyses will use SAS[®] version 9.3 or higher. Summary tables will be presented by treatment group, and will include a pooled group comprising of both anifrolumab regimens. Treatment groups will be presented in the following order: anifrolumab basic regimen, anifrolumab intensified regimen, all anifrolumab and placebo. For continuous endpoints, data only up to IP discontinuation will be analysed. If IP has not been reported as prematurely discontinued, available data up to and including Week 104 will be used for continuous endpoints analyses. Otherwise, the date of IP discontinuation will be determined as the date of last IP administration. However, all subjects who have an infusion of IP within the Week 48 analysis visit window will be determined to have completed treatment in the double-blind treatment period, and their Week 52 data will be included in the analyses. Additionally, subjects who are determined to have completed treatment and have a Week 52 visit will not be imputed as non-responders at Week 52 for discontinuation of IP. The treatment policy sensitivity analysis of 24-hour UPCR will be analysed using all available data. Data (including derived variables) will be presented in listings sorted by treatment group and subject number.

Unless otherwise noted, categorical data will be presented using counts and percentages with the denominator for percentages being the number of subjects in the analysis set by treatment group. Percentages will be rounded to one decimal place; except 100% which will be displayed without any decimal places. Percentages will not be displayed for zero counts.

Unless otherwise noted, continuous variables will be summarised using the number of observations (n), mean, standard deviation (SD), median, minimum, and maximum. The minimum and maximum values will be displayed to the same level of precision as the raw data, the mean and median to a further decimal place and the SD to two additional decimal places. Any CI's, CVs, geometric means and any quartile values will also be presented to one more decimal place than the raw data.

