4.1.4.3 Non-responder imputation

For the analysis of the secondary and exploratory efficacy responder endpoints (excluding time to modified renal response), subjects will be imputed as non-responders from time at which the criteria are met, in the following cases:

a) Medication criteria

Subjects who meet any of the following medication criteria:

- Subjects who receive any restricted medication (see [Appendix A](#) and [Appendix B](#)) after randomisation or beyond any protocol allowed thresholds will be considered a non-responder from the time the respective medication was administered up to and including Week 104.
- Subjects who meet any of the corticosteroid criteria (see [Appendix B](#)) will be considered a non-responder from the time the condition is met, up to and including Week 24, Week 52, Week 80 or Week 104, depending on the condition and when it is met.
- Subjects who meet any of the MMF criteria (see [Appendix B](#)) will be considered a non-responder from the time the condition is met, up to and including to Week 24, Week 52, Week 80 or Week 104, depending on the condition and when it is met.

b) Discontinued IP

Subjects who prematurely discontinue from IP, including subjects who withdraw from the study. All subjects who have an infusion of IP within the Week 48 analysis visit window will be determined to have completed treatment in the double-blind treatment period.

Non-responder imputation will be applied at all scheduled visits, including missing visits. If a subject does not have a response at a visit, they will be imputed as a non-responder (note that unless IP was discontinued or any of the medication criteria above are met, LOCF will be applied to missing values at the first missed visit in case of consecutive missed visits and the non-responder imputation will be applied to the response values determined after LOCF imputation. See Section 4.1.4.2 for more details on LOCF).

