4.2.2 Analysis of the secondary variable

As a secondary endpoint, a composite endpoint is used to evaluate the effect of anifrolumab on renal response. For this analysis the estimand of interest is the difference in change from baseline at Week 52 in renal response between anifrolumab and placebo, to reflect the effect of the initially assigned IP (full analysis set). This estimand answers a clinically relevant question comparing the number of subjects able to both tolerate therapy sufficiently to remain on treatment to a given point in time and to achieve adequate response without further medication being required. Any missing data will be imputed as defined in Section 4.1.4.

The proportion of subjects achieving CRR in the anifrolumab pooled group will be compared with the placebo group using a CMH approach (Stokes ME, 2012) stratified by:

- Results of IFN test at screening using a 4-gene type I IFN test (IFN test-high versus test-low)
- 24-hour UPCR ≤ 3.0 mg/mg versus >3.0 mg/mg at screening (within 14 days prior to the expected date of randomisation). Without the results of the second (stratification) sample, subjects cannot be randomised. Turn-around time for results from central laboratory is up to 7 days. On rare occasion an extension of 30-day screening window is allowed if re-collection of the sample is necessary or the results needed for randomisation are delayed.

The individual anifrolumab regimens will also be assessed but not as part of the secondary analysis. The analysis can be described as follows:

- There are n_{ij} subjects in each stratum, where i is the stratum, and j is the treatment group. The number of responders is x_{ij} . The proportion of responders is denoted as $p_{ij} = x_{ij} / n_{ij}$.
 Strata with low counts will be pooled with adjacent strata. If a sub-stratum within the IFN-low stratum has less than 16 subjects (in the pooled treatment group, i.e. placebo pooled with the respective anifrolumab group that is tested), then the two IFN-low sub-strata will be pooled together. If a sub-stratum within the IFN-high stratum has less than 16 subjects (in the pooled treatment group), then the two IFN-high sub-strata will be pooled together. If the two IFN-low sub-strata are pooled together and the two IFN-high sub-strata are pooled together, and any of these strata has less than 16 subjects (in the pooled treatment group) then all strata will be pooled together.

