 - Uncertain – its right limit is the expected number of subjects that have had their values imputed as non-response values in the placebo arm which would have been responders if not permanently discontinued IP early (based on the active response rate in the observed cases);
 - Unlikely – it is the region to the right of the uncertain region.
- Biopsy sensitivity analysis: Based on the main analysis it excludes any subjects whose adjudicated kidney biopsy results show them to be ineligible for study entry.

Subgroup analyses will be performed as described in Section 4.3.

Longitudinal presentations of results over time (i.e. for each post-baseline visit up to Week 104 where CRR based on 24-hour UPCR can be derived) based on the same analysis, with the corresponding 95% CI, will be created. Bar plots showing the proportion of subjects who are responders/non-responders for CRR at Week 24 and Week 52 by treatment group (including CIs and number of subjects included in the analysis) will be provided by 24-hour UPCR at screening (≤ 3 mg/mg and > 3 mg/mg). Additionally, the individual components of CRR will be summarised over time by treatment group.

The proportion of subjects achieving CRR based on 24-hour UPCR at Week 52 and at Week 104 will also be presented in a summary table alongside the proportion of subjects achieving CRR based on spot UPCR at Week 52 and at Week 104 together with a summary of the individual components.

In addition, the time to achieve CRR by treatment group will be presented in a Kaplan-Meier plot including the number of subjects at risk at each visit.

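### Time to CRR is censored when IP stops, although CRR requires staying on IP, so the Kaplan-Meier curve overstates the proportion reaching CRR

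*SAP*

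**What the plan says.** SAP 3.2.1 defines CRR by eGFR, a 24-hour UPCR of at most 0.7 mg/mg, and a third condition: "No discontinuation of IP or use of restricted medication beyond the protocol-allowed threshold before assessment". The same section derives time to CRR as a supportive analysis. A subject who never reaches CRR is censored at the earliest of several dates. Three matter here:

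- the day the subject leaves the study altogether;
- for those whose dosing ended early, the stop itself, worded as "Discontinuation of IP in case of premature discontinuation of IP where the last IP dose is not in the Week 48 analysis visit window";
- for those who stopped early but had their final infusion inside that window, a later date tied to the year 1 endpoint visit, given as "Date of the latest of the Week 52 24-hour UPCR and eGFR observations used in analysis".

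The remaining dates are the Week 104 observations and the database extract. SAP 4.2.2 states the display: "the time to achieve CRR by treatment group will be presented in a Kaplan-Meier plot including the number of subjects at risk at each visit".

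The main CRR analysis handles the same people differently. SAP 4.1.4.3 imputes as non-responders "Subjects who prematurely discontinue from IP, including subjects who withdraw from the study". SAP 4.2.2 describes its question as how many subjects are "able to both tolerate therapy sufficiently to remain on treatment to a given point in time and to achieve adequate response". SAP 4.1.3 makes one exception: subjects dosed in the Week 48 window who have a Week 52 visit "will not be imputed as non-responders at Week 52 for discontinuation of IP".

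Under SAP 1.2.5, subjects who fail the Week 52 continuation criteria receive no further IP. The disposition summary in SAP 4.2.5.1 describes subjects who finish year 1 dosing but do not enter year 2 as having discontinued IP.

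**The concern.** Apart from the Week 52 exception, which the censoring rules already respect, a subject who has stopped IP cannot have the event later. Kaplan-Meier treats a censored subject as someone who could still have it, at the rate seen in those who remain at risk. The curve therefore rises too far after each stop that precedes CRR. This does not depend on the reason for stopping.

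Three things follow.

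- The time-to-event display of the only secondary endpoint would not match the non-responder figures for the same endpoint.
- The gap is likely to be largest after Week 52, when subjects who fail the renal criteria leave the risk set as censored observations.
- If stopping differs between arms, the curves can separate when the proportions reaching CRR do not.

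The two halves of the third CRR condition are also treated differently. Restricted medication is not a censoring reason, so those subjects stay at risk as non-events; stopping IP is censored.

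**Working it through.** The documents state no CRR rate, IP stop rate, year 2 entry rate or expected Kaplan-Meier value, so there is no plan figure to reproduce. The visit schedule is from Protocol 5.1: 24-hour UPCR at Weeks 12, 24, 36, 52, 64, 76, 88 and 104. Every rate below is an assumption.

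At each visit, with n at risk and d first CRRs, Kaplan-Meier multiplies by (1 − d/n). The actual proportion is all first CRRs divided by all subjects.

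**1. Worked arm of 50, to Week 52.** First CRRs are 5, 6, 5 and 4, with 50, 41, 31 and 24 at risk; 4, 4 and 2 subjects stop IP between visits.
- 1 − KM = 1 − (45/50)(35/41)(26/31)(20/24) = 46.3%.
- Actual = 20/50 = 40.0%.

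**2. The same arm to Week 104.** Of the 20 still on IP without CRR, 12 do not enter year 2. One first CRR occurs at each of Weeks 64, 76 and 88, among 8, 7 and 6.
- 1 − KM = 1 − 0.537 × (7/8)(6/7)(5/6) = 1 − 0.537 × 5/8 = 66.4%.
- Actual = 23/50 = 46.0%.

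**3. Range at Week 52.** Response among those at risk is 10, 15, 15 and 15% at the four visits. After Weeks 12, 24 and 36, 8, 10 and 6% of remaining non-responders stop.
- 1 − KM = 1 − 0.90 × 0.85³ = 44.7%, whatever the stop rate.
- Actual, per 100 subjects: 10 respond and 90 × 0.92 = 82.8 remain; 12.42 respond and 70.38 × 0.90 = 63.34 remain; 9.50 respond and 53.84 × 0.94 = 50.61 remain; 7.59 respond. The total is 39.5%.
- Halving or doubling the stop rates gives 42.1% or 34.8%, an excess of 2.7 to 9.9 points.
- If stops occur only in a poor-prognosis 40% (5% response per visit, against 20% in the rest), 1 − KM is 44.1 to 47.0% against 42.0 to 40.5% actual, as the stop rates rise from 8/10/6% to 25/30/20%. The excess is 2.1 to 6.5 points.

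**4. Range at Week 104.** From step 3, 50.61 − 7.59 = 43.02 per 100 are on IP without CRR after Week 52. Suppose 50 to 70% of them do not enter year 2.

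| Response per year 2 visit | 1 − KM | Actual (50% to 70% not entering) |
|---|---|---|
| 15% | 1 − 0.5527 × 0.85⁴ = 71.1% | 49.8% to 45.7% |
| 5% | 1 − 0.5527 × 0.95⁴ = 55.0% | 43.5% to 41.9% |

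For example, with 50% not entering and 15% response: 39.5 + 43.02 × 0.50 × (1 − 0.85⁴) = 49.8. The excess is 11.5 to 25.5 points, or 8.4 to 31.6 points if year 1 stopping is also halved or doubled.

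**5. Between arms at Week 52.** Take a constant response rate per visit and a constant stop fraction after Weeks 12, 24 and 36, solved so that both arms truly reach 40%. With 15% of one arm and 35% of the other stopping before CRR, 1 − KM reads 43.9% and 51.5%: a gap of 7.6 points where there is none.

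**The case against.** The strongest reply is that this is one supportive plot. No test, median or Kaplan-Meier percentage is attached to it, and it is outside the testing hierarchy. The SAP does not say the curve will be read as a proportion. CRR proportions with non-responder imputation are given at each visit, with confidence intervals. This stands and limits the consequence, but one minus Kaplan-Meier is ordinarily read as the proportion responding. Numbers at risk show the thinning without correcting the curve.

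A second reply is that the rule is deliberate. Version 5.0 of the SAP revised the censoring of all time-to-event variables, and a curve censored at IP stop describes the rate of first CRR while on IP. That is a legitimate quantity if labelled so, but the SAP does not label it so. The while-on-treatment strategy in SAP 4.2.1 is stated for continuous endpoints, whereas CRR has its own composite question. That question is written for the Week 52 comparison and does not formally bind the plot. The mismatch is therefore between displays of one endpoint, not a breach of a stated rule for the plot.

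Third, the companion curve in SAP 3.1, time to UPCR of at most 0.7 mg/mg, has matching IP-stop rules, so changing one would separate them. The difference is justified: that event does not require being on IP.

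Fourth, subjects who do not enter year 2 might not count as premature discontinuations. They would still be censored early. Their follow-up ends at Week 60 with no further 24-hour UPCR scheduled (Protocol Table 3), so they leave the risk set before Week 64 either way.

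Finally, the sizes are assumed. That is correct, and because worsening disease is a reason to stop IP, the poor-prognosis case may be the more realistic one at Week 52. It lowers the excess but does not remove it.

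**Conclusion.** The concern holds. Under the SAP's own CRR definition, stopping IP is a competing event, and censoring it biases one minus Kaplan-Meier upward in any arm where a stop before CRR is followed by another subject's first CRR. That direction follows from the arithmetic and needs no assumed rate.

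The size rests entirely on assumptions: roughly 2 to 10 points at Week 52 and 8 to 32 points at Week 104 across the scenarios above. With no stops and full entry to year 2, the two estimates coincide.

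The scope is limited to a supportive, descriptive display. The primary UPCR test, the CRR test, the type I error rate and the visit-wise CRR proportions are unaffected. The change should be made because it costs little and the display concerns the only secondary endpoint.

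**What to change.** In SAP 3.2.1 and 4.2.2, treat the following as a competing event for time to first CRR:

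- premature IP discontinuation, dated at the Week 52 observation if the last dose is in the Week 48 window;
- study withdrawal;
- non-entry to year 2, dated at the Week 52 observation.

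Censor only subjects still on IP without CRR, at the Week 104 observation or the database extract date. Plot the Aalen-Johansen cumulative incidence of first CRR by arm.

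Alternatively, keep all such subjects in the risk set as non-responders to the scheduled Week 104 date, or to the extract date if earlier. Keeping them only to Week 52 is not enough. In step 4, with 60% not entering year 2 and 15% response per visit, that gives 1 − (1 − 0.395) × 0.85⁴ = 68.4% at Week 104, against 47.7% actual.

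Label the plot as time to first CRR, which differs from CRR at a visit because a subject can reach CRR and lose it. If the existing curve is kept as well, label it as response while on IP, not as a proportion responding.

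The cost is SAP wording and a different plotting routine. No new data are needed: IP discontinuation dates are already used for censoring, and non-entry to year 2 is already needed for the disposition tables in SAP 4.2.5.1.

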3.3 Exploratory outcome variables

3.3.1 CCI [Redacted]

[Redacted]

3.3.2 CCI [Redacted]

[Redacted]

- | [Redacted]
 - | [Redacted]
- | [Redacted]
 - | [Redacted]
- | [Redacted]
 - | [Redacted]

3.3.3 CCI [Redacted]

[Redacted]

3.3.4 CCI [Redacted]

[Redacted]

- | [Redacted]
 - | [Redacted]
 - | [Redacted]
- | [Redacted]
 - | [Redacted]

- CCI

3.3.5 Alternative complete renal response

To evaluate the effect of anifrolumab compared with placebo on renal response in LN subjects when urine sediment is considered in the definition, the proportion of subjects achieving aCRR at Week 52 and Week 104 will be used. A subject achieves aCRR if all of the following criteria are met:

- eGFR:
 - ≥ 60 mL/min/1.73 m² or no confirmed decrease of eGFR from baseline of $\geq 20\%$
- 24-hour UPCR ≤ 0.7 mg/mg
- Inactive urine sediment (defined as < 10 RBC/hpf)
- No discontinuation of IP or use of restricted medication beyond the protocol-allowed threshold before assessment. Allowed restricted medications are defined in [Appendix A](#) and [Appendix B](#).

3.3.6 Graded alternative complete renal response

The effect of anifrolumab compared with placebo on renal response in LN subjects will also be further assessed using the difference in proportions of subjects achieving graded aCRR at Week 52 and of subjects achieving graded aCRR at Week 104. A subject achieves graded aCRR only if all following criteria are met:

- A decrease in 24-hour UPCR:
 - For subjects with baseline UPCR > 3 mg/mg: UPCR ≤ 1 mg/mg
 - For subjects with baseline UPCR ≤ 3 mg/mg: UPCR ≤ 0.7 mg/mg
- eGFR:
 - ≥ 60 mL/min/1.73 m² or no confirmed decrease of eGFR from baseline of $\geq 20\%$
- Inactive urine sediment (defined as < 10 RBC/hpf)
- No discontinuation of IP or use of restricted medication beyond the protocol allowed threshold before assessment. Restricted medications are defined in [Appendix A](#) and [Appendix B](#).

3.3.7 Sustained reduction of oral corticosteroid dose

The effect of anifrolumab compared with placebo on the ability to reduce the OCS dose will be assessed in subjects with baseline OCS ≥ 20 mg/day prednisone-equivalent. Sustained reduction of OCS dose is assessed using the difference in proportions of subjects meeting all the following criteria:

- Achieve an OCS dose of ≤ 7.5 mg/day prednisone-equivalent by Week 24
- Maintain an OCS dose ≤ 7.5 mg/day prednisone-equivalent from Week 24 to Week 52
- No discontinuation of IP or use of restricted medication beyond the protocol-allowed threshold before assessment. Allowed restricted medications are defined in [Appendix A](#) and [Appendix B](#).

The proportion of subjects achieving OCS tapering requirement will also be assessed at Week 104:

- Achieve an OCS dose ≤ 5.0 mg/day prednisone-equivalent by Week 80
- Maintain an OCS dose ≤ 5.0 mg/day prednisone-equivalent from Week 80 to Week 104
- No discontinuation of IP or use of restricted medication beyond the protocol allowed threshold before assessment. Allowed restricted medications are defined in [Appendix A](#) and [Appendix B](#).

The standardised area under the curve (AUC) of OCS dose up to Week 52, up to Week 104, and from Week 52 to Week 104 will be calculated as follows:

For each single daily dose, the duration of the single dose will be calculated as end date – start date + 1. If the start date is before Day 1, Day 1 will be used instead for calculating the AUC up to Week 52 and up to Week 104. If the start date is before the date of Week 52 (date of Visit 14), the date of Visit 14 will be used instead for calculating the AUC from Week 52 to Week 104. If the end date is after the date of Week 52 (date of Visit 14) or after the date of Week 104 (date of visit 29), the date of Visit 14 and Visit 29 respectively will be used instead for calculating the AUC up to Week 52 and Week 104. The AUC for each single dose will be derived by the daily dose (mg/day) multiplied with the duration (days). The AUC is the sum of the AUCs of the single doses. The AUC of OCS dose will only be calculated if all necessary data are available up to Visit 14 (i.e., daily prednisone equivalent OCS dose can be calculated) or Visit 29 respectively. For subjects who discontinued IP before Visit 14 or Visit 29 respectively, the AUC will be calculated up to the date of discontinuation of IP. If a subject does not receive any OCS dose (i.e., no corresponding medication documented) the AUC for this subject will be set to 0. The standardised AUC will be derived as:

- For standardised AUC up to Week 52: AUC divided by the available days (date of Visit 14 / date of discontinuation of IP – date of Day 1 + 1) multiplied by 364 (52 weeks).
- For standardised AUC from Week 52 to Week 104: AUC divided by the available days (date of Visit 29 / date of discontinuation of IP – date of Visit 14 + 1) multiplied by 364 (52 weeks).
- For standardised AUC up to Week 104: AUC divided by the available days (date of Visit 29 / date of discontinuation of IP – date of Day 1 + 1) multiplied by 728 (104 weeks).

3.3.8

CCI [Redacted]

[Redacted]

- [Redacted]
- [Redacted]

[Redacted]

- [Redacted]
- [Redacted]

3.3.9

CCI [Redacted]

[Redacted]

3.3.10

CCI [Redacted]

[Redacted]

[Redacted]

- [Redacted]
- [Redacted]
- [Redacted]

[Redacted]

CCI [Redacted]

- [Redacted]
- [Redacted]
- [Redacted]
- [Redacted]

[Redacted]

- [Redacted]
- [Redacted]
- [Redacted]

[Redacted]

[Redacted]

- [Redacted]
- [Redacted]
- [Redacted]
- [Redacted]
- [Redacted]

3.3.11

CCI [Redacted]

[Redacted]

- | [Redacted]
- | [Redacted]
- | [Redacted]
- | [Redacted]
- | [Redacted]
- | [Redacted]

[Redacted]

- | [Redacted]
- | [Redacted]
- | [Redacted]
- | [Redacted]
- | [Redacted]

[Redacted]

CCI [Redacted]

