4 ANALYSIS METHODS

4.1 General principles

4.1.1 Visit windows

For visit based analyses, the variables will be summarised based on the scheduled days with adjusted analysis-defined visit windows. The adjusted analysis-defined windows are summarised below:

Table 2 Visit windows

Adjusted Defined Windows Visit	Scheduled Study Day	Maximum Windows
Day 1	1	Study Day 1
Week 4	29	$2 \leq \text{Study Day} \leq 42$
Week 8	57	$43 \leq \text{Study Day} \leq 70$
Week 12	85	$71 \leq \text{Study Day} \leq 98$
Week 16	113	$99 \leq \text{Study Day} \leq 126$
Week 20	141	$127 \leq \text{Study Day} \leq 154$
Week 24	169	$155 \leq \text{Study Day} \leq 182$
Week 28	197	$183 \leq \text{Study Day} \leq 210$

Adjusted Defined Windows Visit	Scheduled Study Day	Maximum Windows
Week 32	225	211 ≤ Study Day ≤ 238
Week 36	253	239 ≤ Study Day ≤ 266
Week 40	281	267 ≤ Study Day ≤ 294
Week 44	309	295 ≤ Study Day ≤ 322
Week 48	337	323 ≤ Study Day ≤ 350
Week 52	365	351 ≤ Study Day ≤ 378
Week 56	393	379 ≤ Study Day ≤ 406
Week 60	421	407 ≤ Study Day ≤ 434
Week 64	449	435 ≤ Study Day ≤ 462
Week 68	477	463 ≤ Study Day ≤ 490
Week 72	505	491 ≤ Study Day ≤ 518
Week 76	533	519 ≤ Study Day ≤ 546
Week 80	561	547 ≤ Study Day ≤ 574
Week 84	589	575 ≤ Study Day ≤ 602
Week 88	617	603 ≤ Study Day ≤ 630
Week 92	645	631 ≤ Study Day ≤ 658
Week 96	673	659 ≤ Study Day ≤ 686
Week 100	701	687 ≤ Study Day ≤ 714
Week 104	729	715 ≤ Study Day ≤ 742
Week 108	756	743 ≤ Study Day ≤ 770
Week 112	784	771 ≤ Study Day ≤ 798

For assignment of data to time points using the visit windows, study day will be defined as (Date of assessment – date of first administration of IP) +1. Using this definition, the day of first dose of IP will be Day 1 and the scheduled visit date of Week 4 will be study day 29 (=28+1) for example.

If multiple readings are recorded within a single visit window, the following rules will be followed.

- If there are two or more observations within the same visit window, then the non-missing one closest to the scheduled visit will be used in the analysis.
- If two observations are equidistant from the scheduled visit, then the non-missing observation with the earlier collection date will be used in the analysis.
- If two observations are collected on the same day, then the non-missing one with the earlier collection time will be included in the analysis.

[figure not shown]
If a visit window does not contain any observations, then the data will remain missing.

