Furthermore, the standardised AUC up to Week 52, up to Week 104 and from Week 52 to Week 104 will be summarised by treatment group for all subjects.

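### SAP 3.3.7 does not limit the OCS AUC to records that overlap the window, so the literal rule gives negative durations, and the Week 52 to Week 104 divisor fails for subjects who stopped IP before Visit 14 (minor)

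*SAP*

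**What the plan says.** SAP 3.3.7 defines three standardised AUCs of OCS dose: up to Week 52, up to Week 104, and from Week 52 to Week 104. All three are built from medication records.

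- **Duration.** "For each single daily dose, the duration of the single dose will be calculated as end date – start date + 1".
- **Start dates.** "If the start date is before Day 1, Day 1 will be used instead for calculating the AUC up to Week 52" (and likewise up to Week 104). For the Week 52 to Week 104 AUC, "If the start date is before the date of Week 52 (date of Visit 14), the date of Visit 14 will be used instead".
- **End dates.** For records running past the visit, "the date of Visit 14 and Visit 29 respectively will be used instead for calculating the AUC up to Week 52 and Week 104".
- **Aggregation.** "The AUC is the sum of the AUCs of the single doses".
- **Standardisation.** The Week 52 to Week 104 sum is divided by the days from Visit 14 to Visit 29, or to IP discontinuation for those who stopped earlier, counting both ends. It is then multiplied by 364.

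SAP 4.2.3.3 adds that the AUC "from Week 52 to Week 104 will be summarised by treatment group for all subjects".

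**The concern.** Moving a start date up to the window limit is correct for a record that straddles the limit. It is wrong for a record that had already ended: the start is moved past the end, and the duration becomes negative. Moving an end date back has the same effect on a record that had not yet begun. Nothing in SAP 3.3.7 leaves such records out or sets their duration to zero.

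These records would be common. SAP 1.2.3 requires tapering in the first year, so most subjects should have several OCS records that end well before Visit 14. Full completers are affected as well as early discontinuers. The higher and longer the earlier dose, the larger the amount subtracted.

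The divisor is a separate fault. A subject who stopped IP before Visit 14 has no on-IP time between Week 52 and Week 104, yet the SAP neither excludes that subject nor says that the value is missing.

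**Working it through.** **Inputs.** Visit 14 is Day 365 and Visit 29 is Day 729, the scheduled days in SAP Table 2; the Week 52 window there is "351 ≤ Study Day ≤ 378". The documents state no AUC value, so there is no figure to reproduce. The dose histories are assumptions. They respect the 40 mg/day entry limit in SAP 1.2.1 and follow the taper goals in SAP 1.2.3 and 1.2.4 (10 mg/day by Week 12, 7.5 mg/day by Week 24, 5 mg/day at Week 80).

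**When the sign turns.** In the Week 52 to Week 104 AUC, a record ending on Day e before Visit 14 has duration e − 365 + 1, which is negative for e ≤ 363. In the AUC up to Week 52, a record starting on Day s after Visit 14 has duration 365 − s + 1, which is negative for s ≥ 367.

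**Illustrative completer, Week 52 to Week 104.**

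| Dose (mg/day) | Days | Literal duration | Literal mg | Overlap mg |
|---|---|---|---|---|
| 30 | 1–14 | 14 − 365 + 1 = −350 | −10,500 | 0 |
| 20 | 15–42 | 42 − 365 + 1 = −322 | −6,440 | 0 |
| 10 | 43–84 | 84 − 365 + 1 = −280 | −2,800 | 0 |
| 7.5 | 85–400 | 400 − 365 + 1 = 36 | 270 | 270 |
| 5 | 401–729 | 729 − 401 + 1 = 329 | 1,645 | 1,645 |
| Sum | | | −17,825 | 1,915 |

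Available days are 729 − 365 + 1 = 365. Multiplying by 364/365 gives −17,776 mg under the literal rule and 1,910 mg with overlap only.

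The sign does not depend on the exact visit day. With Visit 14 on Day 351, the literal sum is −10,080 − 6,160 − 2,660 + 375 + 1,645 = −16,880 mg. On Day 378 it is −10,890 − 6,700 − 2,930 + 172.5 + 1,645 = −18,702.5 mg.

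**Same completer, up to Week 52.** The overlap sum is 30×14 + 20×28 + 10×42 + 7.5×281 = 3,507.5 mg. The literal rule adds 5 × (365 − 401 + 1) = 5 × (−35) = −175 mg, giving 3,332.5 mg. Standardised, that is 3,323 mg against 3,498 mg.

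**Other tapers, Week 52 to Week 104, unstandardised.** The first three histories take the starting dose on Days 1–84, 10 mg on Days 85–168, 7.5 mg on Days 169–560 and 5 mg on Days 561–729. Overlap only gives 7.5×196 + 5×169 = 2,315 mg for any starting dose.

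- 20 mg start: 20×(−280) + 10×(−196) + 2,315 = −5,245 mg.
- 30 mg start: −8,400 − 1,960 + 2,315 = −8,045 mg.
- 40 mg start: −11,200 − 1,960 + 2,315 = −10,845 mg.
- 10 mg to Week 12, then 7.5 and 5 mg: 10×(−280) + 2,315 = −485 mg.
- 10 mg to Week 24, then 7.5 and 5 mg: 10×(−196) + 2,315 = +355 mg.
- 7.5 mg to Week 40, then 5 mg: 7.5×(−84) + 1,825 = +1,195 mg, against 1,825 mg.
- One constant-dose record over both years: no error.

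The AUC up to Week 104 is correct in all of these histories.

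**Divisor.** With IP stopped on Day 364, available days are 364 − 365 + 1 = 0. With IP stopped on Day 169, they are 169 − 365 + 1 = −195. A negative sum over a negative divisor is positive, so a check for negative values would not catch it.

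**The case against.** The strongest reply is that the window titles already settle the matter. An AUC from Week 52 to Week 104 cannot include a course that ended in the first year, and the date replacements are ordinary clipping of records that cross a limit. A negative cumulative dose is impossible, and a programmer would probably see it on the first run. The phrase about all subjects in SAP 4.2.3.3 may only contrast with the sustained-reduction endpoint, which is limited to baseline OCS of at least 20 mg/day.

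Much of this stands: the intent is clear, and the likely outcome is a quiet repair. But the SAP writes such exclusions elsewhere. SAP 3.6.1 says which herpes zoster events are not considered, and SAP 3.5.4 removes a one-day double count of medication. SAP 3.3.7 has no equivalent and refers to no appendix for the AUC. Flooring durations, dropping records, setting values to missing and excluding subjects do not all give the same values or the same N. Even on the narrower reading of SAP 4.2.3.3, who belongs in the Week 52 to Week 104 summary is not defined.

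A reader might also infer that OCS courses ending before Day 1 enter the sum, because Protocol 4.1.3 collects all earlier SLE and LN drugs. That is a collection rule, and SAP 3.5.4 classes a course that ended before first dose as prior medication only. The documents do not show that such records feed an on-study AUC.

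**Conclusion.** The derivation is wrong as written. The AUCs up to Week 52 and from Week 52 to Week 104 are understated for subjects whose dose changed so as to leave a record outside the window. The second is often negative for subjects tapered from 20–40 mg/day. The Week 52 to Week 104 divisor is zero or negative for anyone who stopped IP before Visit 14.

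Three stronger readings are not supported:

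- **Every tapering subject goes negative.** Low starting doses or small late tapers leave a positive value that is too low.
- **A steroid-sparing conclusion rests on this AUC.** The defined OCS endpoint is the sustained-reduction proportion, compared by CMH. The AUC is only summarised, alongside dose by visit and shift plots.
- **The error favours one arm.** The documents give no dose data by arm from which to judge that.

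The primary analysis, the secondary analysis and the sustained-OCS-reduction endpoint are untouched. Severity is minor. The sizes rest on assumed dose histories and scheduled visit days. They also assume that no appendix outside the supplied text holds a record-selection rule for the AUC.

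**What to change.** Amend SAP 3.3.7 in two places.

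1. Define each record's duration as max(0, min(end, window end) − max(start, window start) + 1). The window end is the visit date, or the IP discontinuation date where the section already stops the AUC there. This also supplies the record-level rule now missing for discontinuers, and it keeps numerator and divisor on the same window.
2. Compute the Week 52 to Week 104 AUC only for subjects who received IP in the second-year extension, and report its N by treatment group. Align the wording in SAP 4.2.3.3.

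The cost is two sentences and minor programming. No new data are needed.
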